#### **5.6.2.1.3 Infusion-Related Reactions**

Pembrolizumab can cause severe infusion-related reactions. For severe and life-threatening infusion reactions, pembrolizumab should be discontinued; for mild or moderate infusion reactions the infusion should be interrupted, or the rate of infusion slowed. Immediate access to an Intensive Care Unit or equivalent environment and resuscitation equipment and appropriate medical therapy (including epinephrine, corticosteroids, IV antihistamines, bronchodilators, and oxygen) must be available to treat infusion-related reactions.

All Grade 3 or 4 infusion reactions should be reported within 24 hours to HUYABIO Medical Monitor and reported as a serious adverse event (SAE) if criteria are met. Infusion reactions should be graded according to NCI-CTCAE guidelines.

#### **5.6.2.1.4 Severe Hypersensitivity Reactions**

If a hypersensitivity reaction occurs, the subject must be treated according to the best available medical care. Subjects should be instructed to report any delayed reactions to the Investigator immediately based on the appropriate complete guideline for emergency treatment of anaphylactic reactions.

Corticosteroids can be administered intravenously. The subject should be placed on a monitor immediately and the Intensive Care Unit must be alerted for possible transfer if needed. Investigators should withhold a dose as described in the KEYTRUDA® USPI (Dose Modifications).

## **6 STUDY ASSESSMENTS AND PROCEDURES**

The procedures and assessments to be performed during each period of the study are outlined in the Schedule of Dosing and Assessments ([Table 1](#)) and described in the following section.

### **6.1 Study Visits and List of Procedures**

#### **6.1.1 Screening Assessments (within 28 days prior to start of treatment)**

Written informed consent for participation in the study must be obtained before performing any study-specific screening tests or evaluations. Informed Consent Forms (ICFs) for all subjects screened will be maintained at the study site.

Screening assessments will be performed within 28 days prior to Day 1. Results of standard of care tests or examinations performed prior to obtaining informed consent and within 28 days prior to Day 1 may be used (and do not need to be repeated during screening unless they do not meet the criteria defined in the protocol).

The following will be collected or performed between Day -28 and Day -1:

- Written informed consent

- Inclusion/exclusion criteria review for confirmation of eligibility
- Medical history, concomitant medications, baseline signs and symptoms, demographics, and height
- HBsAg and anti-HCV serology tests
- Cancer diagnosis history including histological diagnosis, PD-L1 expression, known mutation status for B-Raf proto-oncogene serine/threonine kinase gene (BRAF) V600, EGFR, and ALK and treatment history
- Brain magnetic resonance imaging (MRI) if clinically indicated, and radiographic tumor assessment. If a subject has metal implants, a computerized tomography (CT) scan should be used instead of an MRI.

#### **6.1.2 Baseline Assessments (within 14 days prior to start of treatment)**

Baseline assessments may be completed within 14 days before C1D1. If there is any history or findings suggestive of significant heart disease, a cardiology consultation should be obtained. Women of childbearing potential must have a negative serum pregnancy test at baseline within 14 days of start of treatment per the Schedule of Dosing and Assessments ([Table 1](#)).

Baseline assessments include a complete physical examination, vital signs, ECOG performance status, weight, concomitant medications, laboratory tests (hematology, chemistry, coagulation and urinalysis), serum pregnancy test (if applicable), and ECG.

All screening and baseline assessments must be completed and reviewed to confirm that subjects meet all eligibility criteria. Subject registration and ESF approval will be obtained in accordance with Section [4.3](#).

#### **6.1.3 Treatment Phase Assessments**

Cycle 1 Day 1: physical exam, vital signs, ECOG performance status, weight, concomitant medications, and laboratory assessments will be performed according to the Schedule of Dosing and Assessments ([Table 1](#)).

All visits and assessments from Cycle 2, Day 1 onwards may be performed  $\pm 3$  days from the date of the projected visit date. First assessment of tumor response will be scheduled on C3D1 and every 6 weeks ( $\pm 3$  days) thereafter, or sooner if a subject develops clinical signs and symptoms of disease progression, until disease progression or end of study treatment.

#### **6.1.4 End of Treatment (EoT) Safety Visit Assessments**

The EoT safety follow-up visit will be conducted 30 ( $\pm 3$ ) days following the last dose of HBI-8000, or before the initiation of new cancer treatment, whichever is earlier. Assessments will include a physical examination, vital signs, ECOG performance status, weight, concomitant medications, laboratory tests (hematology, chemistry, coagulation and urinalysis), serum pregnancy test (if applicable), ECG, and assessment of any ongoing adverse events.

Subjects with HBI-8000-related AEs of Grade  $\geq 2$  observed at the EoT visit should be followed-up and assessed monthly until the AEs have resolved to Grade  $\leq 1$  or are determined to be chronic or subject receives other anti-cancer therapy.

Any pregnancies while on this study or within 28 days of the last dose of HBI-8000 will be followed up, with female subject's permission, until the birth of the baby (Refer to Section [6.2.2.4.8](#)).

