## **3 STUDY DESIGN**

### **3.1 Overall Design**

This is a multicenter, open label, non-randomized, Phase 2 study of HBI-8000 in combination with a Food and Drug Administration (FDA) approved dose of pembrolizumab as the first checkpoint inhibitor therapy for advanced or metastatic NSCLC where subjects have programmed death ligand 1 (PD-L1) expression Tumor Proportion Score (TPS)  $\geq 1\%$ . Prior to enrollment, the PD-L1 expression status must be available. Historical data may be used to assess for eligibility. If historical data is not available, tumor tissue will be analyzed locally by an FDA-approved test to yield PD-L1 status prior to enrollment.

The dose of HBI-8000 is 30 mg twice weekly. Pembrolizumab is administered according to prescribing information.

The study will include a screening period of up to 28 days before the first dose of HBI-8000. Study Treatment may be with or without pembrolizumab. HBI-8000 and pembrolizumab will continue up to 24 months. HBI-8000 will continue until disease progression, unacceptable toxicity related to HBI-8000 ensues or withdrawal of informed consent to receive HBI-8000.

The Treatment Phase allows for up to 24 months of treatment (cycles are 21 days), providing the subject does not experience disease progression or unacceptable toxicity. An End of Treatment safety visit will be performed 30 ( $\pm 3$ ) days after last dosing of HBI-8000. If HBI-8000 is discontinued due to unacceptable toxicities related to HBI-8000, pembrolizumab may continue as single agent under standard of care. Subjects will be followed for up to 12 months after the last dose of HBI-8000 for disease status, including initiating a new cancer treatment and experiencing disease progression, death, or becoming lost to follow-up or consent withdrawal.

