## **3.3      End of Treatment Definition**

The end of treatment is defined as the date of the last dose of HBI-8000 taken by the subject.

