#### **6.2.2.4.6 Follow-Up of Adverse Events**

Subjects should be asked to specifically describe any signs, symptoms, or AEs (regardless of relationship to Study Treatment) they may notice prior to the start of the study or thereafter. At a minimum, subjects should be asked to report any changes at each visit to the study center. Conditions that the subject experienced prior to informed consent should be recorded in the medical history section of the eCRF.

AEs, Grade 2 and above, considered to be at least possibly related to the Study Treatment must be followed up after the EoT assessment until the events have resolved, returned to the baseline level, are judged by the Investigator to be stable, or no longer require follow up provided the subject is withdrawn from the study due to initiation of new therapy or consent withdrawal for further follow-up. AEs that are assessed by the Investigator as unrelated to Study Treatment will be followed only to the EoT visit. The outcome of any AEs which do not resolve will be recorded as "ongoing" on the eCRF.

Serious adverse events (SAE) and adverse events of special interest (AESI), namely immune-related toxicities, will be collected for up to 90 days following cessation of treatment or 30 days following cessation of treatment if the subject initiates new anticancer therapy, whichever is earlier.

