### 7.5.2.1 Adverse Events

Adverse events will be coded using the MedDRA classification system version 24.0 or higher. The severity of the events will be graded by the Investigator according to the NCI CTCAE version 5.0 or higher.

All adverse events (AEs) will be summarized, and emphasis will be placed on treatment-emergent adverse events (TEAEs). An AE will be considered treatment-emergent if it occurs or worsens in severity from pre-treatment state on or after the first dose date of any study treatment through 30 days after the last dose of any study treatment. All AEs will be listed.

An overall summary of AE will be provided by the frequency and percentage of subjects experiencing an AEs by MedDRA systems organ class (SOC) and preferred term (PT). TEAEs will be summarized by the frequency and percentage of subjects experiencing TEAEs SOC and

PT, and by worst NCI CTCAE severity grade. Summaries will also be provided for treatment related TEAEs, namely, those judged by the Investigator to be at least possibly related to study drug treatment.

Adverse events resulting in discontinuation from treatment or withdrawal from the study, Grade 3 or higher, serious adverse events, and deaths on-study will be tabulated.

All AEs noted during the study will be listed per subject, detailing reported term, system organ class, preferred term, start date, stop date, severity, relationship to each Treatment, TEAE flag, and outcome.

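### The TEAE window has no cut at new anticancer therapy, so next-line SAEs and AESIs enter the all-cause safety tables while non-serious events on the same days have no scheduled collection

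*Combined protocol and SAP*

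**What the plan says.** Four rules in the combined protocol and SAP meet here.

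- **Visit timing.** Section 6.1.4 sets the EoT safety visit at 30 (±3) days after the last HBI-8000 dose, "or before the initiation of new cancer treatment, whichever is earlier". Table 1 (footnote b) and Sections 4.4.1 and 7.5.1 repeat the rule. In Table 1 the adverse-event row ends at the EoT column; the survival follow-up column has no entry for it.
- **Collection.** Section 6.2.2.4.6 collects SAEs and AESIs for up to 90 days, or "30 days following cessation of treatment if the subject initiates new anticancer therapy, whichever is earlier". For the rest it says: "AEs that are assessed by the Investigator as unrelated to Study Treatment will be followed only to the EoT visit".
- **Analysis window.** Section 7.5.2.1 makes an event treatment-emergent if it occurs or worsens "on or after the first dose date of any study treatment through 30 days after the last dose of any study treatment". Starting another anticancer therapy does not shorten this window.
- **Tables.** Section 7.5.2.1 plans all-cause summaries, including Grade 3 or higher events and SAEs, and a separate summary of treatment-related TEAEs, meaning "those judged by the Investigator to be at least possibly related to study drug treatment".

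Section 3.1 has subjects followed for disease status, "including initiating a new cancer treatment and experiencing disease progression". The start of a next regimen is therefore already something the study tracks.

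**The concern.** Moving the EoT visit ahead of new therapy shows that the protocol sees the confounding. Section 6.1.4 also ends the monthly follow-up of HBI-8000-related events once another anticancer therapy is given. The analysis definition has no matching rule. After a subject starts a next regimen, the days up to day 30 still count as treatment-emergent time on HBI-8000 plus pembrolizumab, and only serious events and AESIs have a defined collection period in them.

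Two things follow. Events of another regimen can appear in the combination's all-cause tables. The same days are also ascertained unevenly, so those tables mix full collection on treatment with partial collection afterwards.

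Safety is a secondary objective, there is no control arm to show a background rate, and the only quantitative argument for the sample size is the chance of seeing an event in at least one subject. On that criterion, one misplaced event counts as a detection. Section 1.1.3.3 names myelosuppression as an important identified risk of HBI-8000. If the next regimen also lowers blood counts (an assumption), a cytopenia caused by it would look like an expected study-drug effect in the all-cause tables.

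**Working it through.** **1. The plan's own safety figure.** Section 7.1 and Table 4 give the probability of at least one event as 1 − (1 − p)^n. At p = 10%: 1 − 0.9^20 = 87.8% and 1 − 0.9^24 = 92.0%, as stated. The point here does not alter Table 4.

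**2. The rules side by side**, for a subject who stops both drugs on day 0 and starts new therapy on day s, before day 30:

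| Item | Ends at | Source |
|---|---|---|
| Last scheduled AE assessment | EoT visit, before day s | Table 1, 6.1.4 |
| Follow-up of unrelated AEs | EoT visit, before day s | 6.2.2.4.6 |
| SAE and AESI collection | day 30 | 6.2.2.4.6 |
| TEAE window | day 30 | 7.5.2.1 |

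An SAE or AESI with onset from day s to day 30 is collected and meets the TEAE definition. No section removes or flags it.

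**3. Length of the overlap.** Days = 30 − s.
- s = 1: 29 days
- s = 7: 23 days
- s = 14: 16 days
- s = 21: 9 days
- s = 28: 2 days

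**4. Weight of one subject.** 1/24 = 4.2 points; 1/20 = 5.0 points. A subject already counted in a given table row adds nothing to it, so these are maxima per row.

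**5. Possible number of subjects.** Two inputs are not in the documents and are assumed: f, the share of subjects starting new therapy inside the window, and q, the chance that such a subject has a new SAE or AESI in the overlap. With m = f × n rounded to whole subjects, the expected extra count is m × q, and the chance of at least one is 1 − (1 − q)^m.

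| f, q | m (n=20 / n=24) | Expected extra subjects | Points | Chance of at least one |
|---|---|---|---|---|
| 10%, 5% | 2 / 2 | 0.1 / 0.1 | 0.5 / 0.4 | 9.8% / 9.8% |
| 25%, 10% | 5 / 6 | 0.5 / 0.6 | 2.5 / 2.5 | 41% / 47% |
| 50%, 20% | 10 / 12 | 2.0 / 2.4 | 10 / 10 | 89% / 93% |

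**6. Anchor.** Section 3.3 states: "The end of treatment is defined as the date of the last dose of HBI-8000 taken by the subject". The EoT visit follows that date, whereas the TEAE window follows the last dose of either drug if pembrolizumab counts as study treatment. Sections 3.1 and 4.5 allow pembrolizumab to go on alone after HBI-8000 stops. In such a subject the TEAE window can run well past the EoT visit. Steps 2 and 3 assume that both drugs stop on the same day.

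**The case against.** The best case for leaving the rule alone has several parts.

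- **Timing is not attribution.** TEAE status is a timing label. Causality is graded separately for each drug, and related TEAEs have their own table. An event plainly due to the next regimen should stay out of that table. This stands, and it confines the problem to the all-cause tables. The protection is weaker where toxicities overlap.
- **A fixed window is conservative.** Shortly after the last dose, HBI-8000 or pembrolizumab may still contribute to an event, and a cut could lose it. This is a good reason to keep collecting to day 30, to retain related events, and to show the uncut count. It does not justify reporting only the uncut count.
- **Detail is left to the SAP.** Section 7 allows the SAP to refine the plan before database lock. But Section 7.5.2.1 already states an explicit rule, and no SAP text in the documents changes it.
- **Subjects may be withdrawn when new therapy begins** (Section 4.4.1). Section 6.2.2.4.6 still sets SAE and AESI collection to day 30 in that case.

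A reader might infer that the two regimens' events can never be separated. The documents do not support this: Section 7.5.2.1 lists every event with its start date and relationship to each treatment, and Section 3.1 follows the start of new therapy. What is missing is a plan to make the split. A reader might also infer that all adverse-event collection stops at the early EoT visit. Section 6.1.4 only times a visit, Section 6.2.2.4 monitors events until resolved or stable, and Section 6.2.2.4.4 gives no end to TEAE reporting. The supportable statement is that new non-serious events after that visit have no scheduled collection.

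**Conclusion.** The point holds for the all-cause TEAE, Grade 3 or higher and SAE tables, and mainly for SAEs and AESIs. As written, Section 7.5.2.1 places events from two regimens in one window with uneven ascertainment, and no split is planned. The treatment-related TEAE table is largely unaffected.

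The size is unknown. One subject is worth at most 4.2 points (n=24) or 5.0 points (n=20) in a row. The expected number of extra subjects, about 0.1 to 2.4, rests wholly on the assumed f and q. It would be tempting to say that most subjects will progress, switch within 30 days and so distort the tolerability result. The documents give no switching rate and no event risk in the overlap, so that reading is unsupported. No decision rule depends on these rates, and the analyses are described as primarily descriptive. This is a cheap improvement to the definition and does not threaten the trial's validity.

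**What to change.** In Section 7.5.2.1, and in the SAP when it is finalised:

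1. For the main all-cause tables, end the TEAE window at the earlier of 30 days after the last dose and the day before new anticancer therapy starts.
2. Keep as treatment-emergent any later event, still within the 30 days, that the investigator rates at least possibly related to HBI-8000 or pembrolizumab.
3. Put the remaining events after new therapy in a separate flagged summary or listing, and show the all-cause count with the uncut 30-day window as a sensitivity analysis, so that no event is lost.
4. State which last dose anchors the window, and say whether pembrolizumab continued alone counts as study treatment for this purpose.

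Leave SAE and AESI collection under Section 6.2.2.4.6 as it is.

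The cost is one clause and one date comparison in the programming, provided that the eCRF holds the start date of new therapy. The downside is that TEAE status after new therapy depends on investigator causality in an open-label study. The sensitivity count makes that dependence visible.

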### **6.1.5 Tumor Status and Survival Follow-up**

After the discontinuation of treatment (HBI-8000), subjects without disease progression will be followed for tumor status with imaging studies of target lesions every 12 ( $\pm 1$ ) weeks until progression, initiation of another anti-cancer treatment, or referral to hospice. Subjects will be contacted every 12 weeks ( $\pm 1$ ) weeks for survival follow-up, until death or end of the study.

## **6.2 Study Procedures Details**

### **6.2.1 Efficacy Assessments**

The following evaluations will be performed throughout the course of the study:

- Tumor response assessments by physical examination and tumor imaging by CT or magnetic resonance imaging (MRI) according to RECIST v1.1: CT scans are the required modality for measurable disease unless a subject has a clinical condition, e.g. severe contrast allergy, when CT without contrast may be used per institution guidelines. The same scanning modality and the same technique must be used to measure each identified and reported lesion at baseline and throughout the study for a given subject.
- Brain magnetic resonance imaging (MRI) if clinically indicated, and radiographic tumor assessment. If a subject has metal implants, a computerized tomography (CT) scan should be used instead of an MRI.

#### **6.2.1.1 Tumor Response Criteria**

All measurable disease (target lesions and non-target lesions) must be documented at screening and reassessed at each subsequent tumor evaluation. Reassessment will be done by imaging studies according to RECIST Guidelines version 1.1 ([Appendix 4](#)), along with physical examinations and other methods as needed. At the Investigator's discretion, CT scans may be repeated at any time if PD is suspected.

Tumor response will be evaluated by the Investigator using the RECIST 1.1 criteria [[Eisenhauer 2009](#)] ([Appendix 4](#)) and recorded in the appropriate eCRFs. Tumor response will also be assessed centrally.

Taking into consideration possible pseudo progression, the subject may continue study treatment until the next imaging evaluation to assess tumor response according to irRECIST criteria. The same scanning modality should be used at baseline and throughout treatment for each subject.

Subjects with isolated CNS progression, but responsive/stable extracranial disease, may remain on the study protocol after consultation with Sponsor Medical Monitor.

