## **Schedule of Events (Dosing and Assessments)**

**Table 1: Schedule of Dosing and Assessments**

Visit	Screening	BL	Cycle 1	Cycle 2	Cycle 3	Cycle 4	≥Cycle 5	EoT Visit b	Survival F/U
Study Day	-28 to -1	-14 to -1	1	1 (±3d) a	1 (±3d)	1 (±3d)	1 (±3d)	30 days post dose b (±3d)	Every 12 Weeks (±1 week)
Informed consent c	X								
Inclusion/Exclusion Criteria	X	X							
Medical History, Baseline Signs and Symptoms, Cancer Diagnosis, and Treatment History d	X								
Demographics, height	X								
Vital signs e	X	X	X	X	X	X	X	X	
Physical exam, weight, ECOG Performance Status	X	X f	X	X	X	X	X	X	
ECG g		X						X	
Brain MRI h	X								
PD-L1 expression TPS i	X								
Hematology j		X	X	X	X	X	X	X	
Coagulation (PT/INR, aPTT)		X						X	
Serum chemistry k and LDH		X	X	X	X	X	X	X	
Urinalysis l		X						X	
Pregnancy test m		X						X	
Hepatitis B and C panel n	X								
HBI-8000 PO BIW o					X				
Pembrolizumab 200 mg infusion p OR Pembrolizumab 400 mg infusion p			X	X	X	X	X		
Tumor assessment q	X				Day 1 of Cycle 3, 5, 7, etc. (every 6 weeks ± 3 days)				
Adverse events r and SAE r				Continuous Assessment				X	
Concomitant medication	X	X		Continuous Assessment				X	
Treatment Compliance			X	X	X	X	X	X	

Visit	Screening	BL	Cycle 1	Cycle 2	Cycle 3	Cycle 4	≥Cycle 5	EoT Visit b	Survival F/U
Study Day	-28 to -1	-14 to -1	1	1 (±3d) a	1 (±3d)	1 (±3d)	1 (±3d)	30 days post dose b (±3d)	Every 12 Weeks (±1 week)
Survival s and Tumor Assessment F/U t									X

Abbreviations: ALT = alanine aminotransferase; aPTT = activated partial thromboplastin time; AST = aspartate aminotransferase; BIW = twice weekly; BL = baseline; BUN = blood urea nitrogen; CT = computed tomography; ECG = electrocardiogram; ECOG = Eastern Cooperative Oncology Group; eCRF = electronic Case Report Form; EoT = end of treatment; F/U = follow-up; HBsAg = hepatitis B surface antigen; INR = international normalized ratio; LDH = lactate dehydrogenase; MRI = magnetic resonance imaging; PO = by mouth; PD = progressive disease; PT = prothrombin time; TSH = thyroid stimulating hormone; T4 = thyroxine

- a. All visits and assessments from Cycle 2 onwards may be performed ± 3 days from the date of the projected visit.

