- b. End-of-Treatment Safety Follow-Up visit, performed 30 ± 3 days after the last day of HBI-8000 administration, or before the initiation of new cancer treatment, whichever is earlier.
- c. Informed consent must be obtained prior to initiation of any study-specific procedures.
- d. Cancer diagnosis must include known mutation status for BRAF V600, EGFR, and ALK.
- e. Temperature, heart rate, diastolic and systolic blood pressure after subject is in a supine position for at least 5 minutes.
- f. Complete physical exam at baseline. Symptom directed physical exam for screening and all other cycles.
- g. Standard 12-lead ECG will be done using local standard procedures at Baseline and at End of Treatment Safety Follow-Up visits.
- h. MRI performed per institutional guidelines and practice, and if clinically indicated for subjects with documented brain metastasis.
- i. Historical data may be used to assess for eligibility. If historical data is not available, tumor tissue will be analyzed locally by an FDA-approved test to yield PD-L1 status prior to enrollment.
- j. Hematology panel to include hemoglobin, hematocrit, red blood cell count, white blood cell count, differential, platelet count.
- k. Chemistry panel to include BUN, creatinine, AST, ALT, LDH, total bilirubin (including direct fraction if total bilirubin abnormal), lipase, amylase, TSH, T4 free (direct), total protein, albumin, uric acid, alkaline phosphatase, sodium, potassium, calcium, magnesium, phosphorus, and glucose.
- l. Urinalysis: dipstick followed by microscopic examination, if abnormal results.
- m. For women of childbearing potential (including those with tubal ligation): Serum pregnancy test at baseline (within 14 days of starting treatment) and at the end of treatment.
- n. Hepatitis B and Hepatitis C testing to include HBsAg, anti-HCV antibodies.
- o. HBI-8000 should be administered twice a week approximately 30 minutes after a meal.
- p. Pembrolizumab 400 mg every 6 weeks or 200 mg every 3 weeks on Day 1 of each Cycle should be administered as intravenous (IV) infusion over 30 minutes and in accordance with the manufacturer package insert and institutional practice.
- q. Tumor assessment of all lesions by radiographic or other modality (CT, MRI). Tumor assessments to be performed at Screening, and Day 1 of Cycles 3, 5, 7, etc. every 6 weeks (± 3 days) thereafter until PD.

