### **2.3.2 Efficacy Endpoints**

Target lesion(s) and non-target lesion(s) will be assessed by imaging studies at screening (baseline assessment), in the last week of Cycle 2 including C3D1, and then every 6 weeks ( $\pm 3$  days) thereafter. Tumor assessments will follow guidelines specified in RECIST criteria v1.1.

- ORR (complete response [CR]+partial response [PR])
- DCR (CR+PR+Stable disease [SD])
- DoR
- PFS

After the discontinuation of HBI-8000 treatment, subjects without disease progression will be followed for progression with imaging of measurable disease every 12 ( $\pm 1$ ) weeks until progression, initiation of another anti-cancer treatment, or referral to hospice whichever occurs first. Survival follow-up will be performed every 12 ( $\pm 1$ ) weeks by telephone contact or e-mail for up to 12 months after the last dose of HBI-8000.

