### **3.1.1      Expected Duration of Subject Participation**

Subject participation duration from screening through end of treatment visit is approximately up to 38 months, including:

Screening period:	Up to 28 days
Treatment period:	Until radiographic disease progression per RECIST v1.1 (assessed by the Investigator), unacceptable toxicity, or other reasons for discontinuation with a maximum treatment duration of 24 months, unless there is an agreement between the Sponsor and the Investigator to allow HBI-8000 beyond 24 months.
Short-term Follow up/ End of treatment (EoT) period	Up to 30 days ( $\pm 3$ days) after the last dose HBI-8000. This will be defined as EoT.
Long-term Follow-up period:	Every 12 weeks (3 months) up to a maximum of 12 months after the last dose of HBI-8000.

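### Subjects kept on study after isolated CNS progression have conflicting scan rules, and section 7.5.1 does not say whether a response after RECIST 1.1 progression counts in ORR

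*Combined protocol and SAP*

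**What the plan says.** **Staying on after progression.** Section 3.1.1 sets the treatment period as "Until radiographic disease progression per RECIST v1.1 (assessed by the Investigator), unacceptable toxicity, or other reasons for discontinuation". Section 6.2.1.1 then makes two exceptions. For possible pseudo-progression, "the subject may continue study treatment until the next imaging evaluation to assess tumor response according to irRECIST criteria". For the CNS, "Subjects with isolated CNS progression, but responsive/stable extracranial disease, may remain on the study protocol after consultation with Sponsor Medical Monitor".

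**Scans.** Two places give an end to on-treatment scanning. Table 1 footnote q has scans "every 6 weeks (± 3 days) thereafter until PD". Section 6.1.3 has them "until disease progression or end of study treatment". Other places give no end:

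- The Table 1 row reads "Day 1 of Cycle 3, 5, 7, etc. (every 6 weeks ± 3 days").
- Section 2.3.2, with matching wording in the synopsis, reads "in the last week of Cycle 2 including C3D1, and then every 6 weeks".
- Section 6.2.1 introduces tumour imaging with "The following evaluations will be performed throughout the course of the study".

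Once HBI-8000 stops, 12-weekly imaging is only for subjects who have not progressed (sections 3.1.2, 6.1.5 and 6.2.1.1.2).

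**Response.** The primary objective (section 2.1) is ORR by RECIST 1.1. Section 7.5.1 names RECIST 1.1 as the primary method and gives iRECIST the task of ruling out suspected pseudo-progression. The endpoint list in the same section then defines ORR by RECIST 1.1 together with irRECIST, and DCR by RECIST 1.1 together with iRECIST. Under Appendix 4, a new lesion is always progression by RECIST 1.1. Under irRECIST it is added to the sum and is not progression in itself.

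**The concern.** **Scans.** A subject retained after isolated CNS progression has, by definition, progressed. A site that works from footnote q would stop scheduled scans for someone who is probably still taking the combination. A site that works from section 2.3.2 would go on scanning. Retention depends on disease outside the CNS being responsive or stable, and on the first reading nothing scheduled checks that this remains true. Scans that were not done cannot be recovered at analysis.

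**Response.** Section 6.2.1.1.1 expects that some responses will follow initial growth or new lesions. The plan therefore foresees the late responder but does not say whether that subject enters the primary ORR. Two analysts could classify the same subject differently. Because the study is open label, the rule is best fixed before such responses are seen.

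**Working it through.** **Step 1: the scan rules side by side, by type of retained subject.**

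| Subject | Basis for staying on | Footnote q and 6.1.3 | Synopsis, Table 1 row, 2.3.2, 6.2.1 | What remains open |
|---|---|---|---|---|
| Isolated CNS progression | 6.2.1.1, after consultation; dosing implied | Scheduled scans end at progression | 6-weekly, no stop | Whether any scheduled scan applies |
| Suspected pseudo-progression | 6.2.1.1, up to the next imaging evaluation | Scheduled scans end at progression | 6-weekly, no stop | The literal conflict with footnote q, and the schedule after that next scan |

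In the second row a further scan is built into the permission itself. The irRC table in Appendix 4 also describes confirmation by two observations at least 4 weeks apart. The repeat CT that section 6.2.1.1 allows when progression is suspected is at the investigator's discretion, so it is not a schedule.

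**Step 2: scheduled scans lost, isolated CNS progression only.** The interval is 6 weeks (Table 1). The documents give no retention time, so the durations are illustrative. Scans lost = weeks on treatment after progression ÷ 6.

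- Strict reading: 6/6 = 1, 12/6 = 2, 24/6 = 4.
- No-stop reading: 0.

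The 12- and 24-week figures do not apply to pseudo-progression, because that permission runs only to the next evaluation.

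**Step 3: effect on ORR.** The plan gives no figure for this point. Its one sample-size figure, in section 7.1, reproduces: 1 − 0.9^20 = 87.8% and 1 − 0.9^24 = 92.0%. It concerns detection of adverse events and serves here only to fix n at 20 to 24.

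The counting rule matters only for a subject with no response before RECIST 1.1 progression and a response after it. Each such subject moves ORR by 1/n:

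- n = 20: 1/20 = 5.0 points
- n = 24: 1/24 = 4.2 points

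The number of such subjects is not in the documents. For 0, 1 or 2 of them, the shift is 0, 5.0 or 10.0 points at n = 20, and 0, 4.2 or 8.3 points at n = 24.

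Section 7.5.1 specifies exact binomial 95% limits. With x responders, the lower limit is the 0.025 quantile of Beta(x, n − x + 1) and the upper limit is the 0.975 quantile of Beta(x + 1, n − x). The responder counts below are illustrative.

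| n | Late responder not counted | Late responder counted |
|---|---|---|
| 20 | 7: 35.0% (15.4 to 59.2) | 8: 40.0% (19.1 to 63.9) |
| 24 | 8: 33.3% (15.6 to 55.3) | 9: 37.5% (18.8 to 59.4) |

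The intervals in the first results column are 59.2 − 15.4 = 43.8 and 55.3 − 15.6 = 39.7 points wide, so one subject's shift is small beside the sampling error.

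**The case against.** **On scans.** A workable reading exists. A subject who stays on protocol is naturally under its 6-weekly schedule. Section 6.2.1.1 requires measurable disease to be reassessed at each later evaluation. The condition on extracranial disease can be checked only by imaging it, and the Medical Monitor is consulted case by case. Section 6.1.3 names two end points without saying which governs, so a site might take the later one. All of this makes continued scanning a reasonable inference. It remains an inference, because footnote q states an explicit stop and carries no exception.

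A reader might go further and infer that everyone treated past progression goes unscanned. The documents do not support that: the pseudo-progression permission is itself defined by a further scan. Nor do they show that scanning of CNS-retained subjects would in fact stop, since several sections say otherwise.

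**On response.** The hierarchy is largely stated: the objective and the method sentence both put RECIST 1.1 first. Section 7.5.1 defers detail to the SAP, and section 7 requires that SAP before database lock, so the rule may yet be settled. This stands as a reason for low severity. The endpoint definition still contradicts the objective as written, and ruling out pseudo-progression can mean either that the first progression is annulled or that it stands. A reader might infer that the primary ORR is meant to be inflated by irRECIST responses. Nothing in the text says so; it leaves the matter open.

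Closing best overall response at first RECIST 1.1 progression is one defensible choice, not the only one. Its merit is that it matches the stated objective.

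**Conclusion.** Two conflicts between stated rules hold, both minor.

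1. For isolated CNS progression, footnote q and section 6.1.3 conflict with the synopsis, the Table 1 row and sections 2.3.2 and 6.2.1. On the strict reading one scheduled scan is lost per 6 weeks of further treatment; on the other reading none is. For suspected pseudo-progression only the literal conflict with footnote q and the schedule beyond the next scan are open.
2. The ORR and DCR definitions in section 7.5.1 do not agree with a RECIST 1.1 primary objective. For ORR this is worth 4.2 to 5.0 points per late responder.

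This rests on three assumptions. Continued dosing after isolated CNS progression is intended, though section 6.2.1.1 does not say it. The efficacy population is close to the 20 to 24 enrolled; a smaller denominator would raise the step above 5.0 points. The number of subjects affected is unknown, since the documents give no rate of isolated CNS progression or of late response, and it may be zero. The study is descriptive, with no ORR threshold and no interim analysis, so no formal decision turns on one responder.

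**What to change.** 1. In Table 1 footnote q and section 6.1.3, replace the stop at progression with a statement that tumour assessments continue every 6 weeks (± 3 days) for as long as study treatment continues, including after progression.
2. In section 7.5.1, define the primary ORR and DCR by RECIST 1.1 alone. Close best overall response at the first RECIST 1.1 progression, isolated CNS progression included. Report irRECIST responses separately as supportive, and use one name for the immune-related criteria throughout.

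The cost is wording in one amendment, carried into the SAP, plus a few extra scans at the existing interval for zero to a few subjects. The primary ORR may be slightly lower, by 4.2 to 5.0 points for each late responder no longer counted. No information is lost, because those responses are still reported.
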